4.2.2 Secondary Outcome Measures

Secondary outcomes include:

- Code status preferences (Aim 1)
- Use of palliative care consult/services (Aim 1)
- Hospice use (Aim 1)
- Health Care Proxy (Aim 1)

Secondary outcomes related to Aim 2a (patients 18+ years admitted to one of the study inpatient units with ADRD/delirium) include:

- Documentation of ACP Preferences in Electronic Health Record

Secondary outcomes related to Aim 2b (caregivers of patients with ADRD/Delirium) include:

- ACP knowledge (Aim 2)
- Confidence in future care (Aim 2)
- Communication satisfaction (Aim 2)
- Decisional satisfaction (Aim 2)
- Decisional conflict (Aim 2)

5 Study Design

This is pragmatic SW-CRT of a PCE-led, video-assisted COVID-19 ACP intervention in inpatient-based units (3 medical-surgical wards, Medical ICU, Cardiac ICU, Neurology ICU, step-down unit) at two hospitals: BMC and North Shore University Hospital (Northwell Health). All inpatients ≥ 65 and all patients with ADRD/Delirium ≥ 18 who are hospitalized on a unit during the intervention phase will receive the intervention.

This 2-year study (2 month data collection and tool preparation, staff training and site standardization (we are already embedded in both health systems doing similar work; thus this

short timeframe is feasible); 16 months rolling recruitment and surveying; 2 months data cleaning and analysis, and 4 months manuscript preparation and dissemination of findings) will roll out the intervention to 14 randomized inpatient units at 2 sites. Every two months, an additional inpatient unit will be added to our intervention at each hospital, i.e., there will be seven waves or "steps"; for a total of 7 units at each hospital.

Consistent with a SW-CRT with two hospital units per step (cluster), prior to the collection of any data in the pre-intervention period, we will generate a set of uniform random numbers for each of the seven clusters to be assigned to a starting period for the study intervention. There will be eight study periods in total with a usual care period at the start of the study for all clusters. The first randomized intervention period will then begin in period two.

Cluster	Baseline	14 Months of Clustered Intervention Expansion							
	M0	M2	M4	M6	M8	M10	M12	M14	
1									
2									
3									
4									
5									
6									
7									

The data needed to assess the outcomes for all patients will be derived from each hospital's EHR (Aim 1).

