For Aim 1, there are special informed consent considerations in this pragmatic SW-CRT: the hospital clinical unit is the level of randomization, the intervention is of low risk and will be implemented as the standard of care for the whole clinical unit, and data for our primary outcome and related outcomes derived from the EHR are ascertained from existing sources. Thus for this aspect of our proposal, we will seek a waiver of individual informed consent and HIPAA authorization after careful review of the criteria to do so as we have previously done successfully in prior studies. The research involves no more than minimal risk to the subjects as described above. We do not believe the waiver will adversely affect the rights and welfare of the subjects. As a pragmatic trial of thousands of hospitalized patients and clinicians, this research could not practicably be carried out without the waiver nor without access to and use of PHI of patients.

For Aim 2a, we will seek a waiver of individual informed consent and HIPAA authorization due to the fact that this is a low risk activity (chart review), and the target population is incapable of consent due to a diagnosis of ADRD/Delirium.

For Aim 2b, verbal informed consent will be obtained for the phone survey. The caregiver survey should take less than fifteen minutes.

Natural Language Processing (NLP) Data Collection

Over the course of the study, we will review the charts for all enrolled participants. For Aim 1 and Aim 2a, the inpatient EHR records (including those with ADRD/Delirium) will be analyzed (approximately 15,000 patients across both sites).

Initial NLP analyses will be done locally at each data collection site (BMC and Northwell) using software that was developed at DFCI for this purpose. The results of that initial analysis will be coded and sent as a HIPAA LDS via HIPAA approved cloud folders such as Box.com to our NLP partners at DFCI. Each site will retain a local mastercode file that will not be shared with anyone outside the institution. Patients will be assigned a unique identifier that will be used on datasets shared with DFCI.

DFCI will have a reliance agreement in place with BUMC and Data Transfer Agreements in place with both BMC and Northwell.

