distributions of the uncertainty and knowledge scale scores, the outcomes of interest between intervention and usual care subjects, as well as the distributional characteristics of all other salient study variables. We will generate descriptive statistics (means, standard deviations, quantiles for continuous variables; counts and percentages for categorical variables) and schematic plots (box-and-whisker, quantile-quantile plots). Given the nature of the cluster randomization that we will employ, we will utilize statistical analytic methods that take the correlated nature of the data into account as well as the influence of time to account for secular trends. In this study, we will examine both the health system and hospital unit as clustering variables, with the hospital unit as the primary clustering variable. We will compare the intervention and usual care groups on salient variables in order to assess balance in the distributions of these variables. Variables found to differ between the study groups will be further evaluated to assess their confounding effects of intervention vs. usual care differences on outcomes in multivariable analyses for correlated (clustered) data.

Aim 1. To test the combined effects of a COVID-19 ACP Educator-led, video-assisted palliative care intervention on rates of: ACP documentation; Medical orders for resuscitation preferences in the EHR; Palliative Care Consults; and, Hospice use. ***Hypothesis: A higher proportion of patients in the intervention phase (vs. control) will: complete ACP documentation (primary trial outcome), have documented orders for resuscitation preferences, have palliative care consults, and enroll in hospice.***

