Primary outcome: ACP documentation. In order to formally estimate and test differences in the proportion of patients with documentation of ACP between the intervention and usual care groups, we will employ logistic regression models for correlated binary outcome data. These models will either involve the use of robust variance methods to account for the clustering of these data by hospital site and/or health system via generalized estimating equations (GEE) or the inclusion of a random effects terms (in which case, the results will be interpreted as cluster-specific). Other potential modifiers of the effect of intervention, confounding variables, or covariates can be added to this model as fixed effects. Although we do not expect effect modification in the study data, we will examine the potential for such effects (interaction) through the use of stratified analyses and the inclusion of interaction terms with study group in our statistical models. Candidate effect modifiers will be specified a priori and will include age, gender, race/ethnicity, religion, and language. We will also examine and incorporate secular trend effects, i.e., the effect of time over the course of the study. Statistically significant interactions with the intervention will be retained and the nature of heterogeneous intervention effects will be estimated using the interaction model.

Based on our prior work in which we exhibited the fact that African-American and Hispanic patients are at particularly high risk for lower level of knowledge related to ACP, not discussing ACP with family, not having a health care proxy, and not having ACP documentation, we anticipate that this intervention may be particularly beneficial for African-American and Hispanic patients.(115, 131, 132) Accordingly, we will evaluate heterogeneous treatment effects by race and ethnicity and anticipate having adequate diversity in our study population to make such assessments. All data regarding Aim 1 will come from the EHR. Our institutions maintain excellent self-report information regarding race and ethnicity.

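### The primary-outcome GEE sentence clusters on hospital or health system (two clusters), which conflicts with the hospital unit named elsewhere and, taken literally with an uncorrected robust test, gives about 40% false positives

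*Combined protocol and SAP*

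**What the plan says.** Four places bear on the clustering level.

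- **Section 12.3, primary outcome.** This is the only paragraph that specifies the model for ACP documentation. It proposes logistic regression for correlated data, with robust variance "to account for the clustering of these data by hospital site and/or health system via generalized estimating equations (GEE". The alternative is "or the inclusion of a random effects terms (in which case, the results will be interpreted as cluster-specific". The hospital unit is not mentioned. No level is given for the random effect and no rule for choosing between the two approaches. Similar procedures are then extended to the other EHR outcomes.
- **Section 12.3, general methods, shortly before the Aim 1 text.** "we will examine both the health system and hospital unit as clustering variables, with the hospital unit as the primary clustering variable".
- **Section 9, Informed Consent.** "the hospital clinical unit is the level of randomization".
- **Section 5, Study Design.** The trial "will roll out the intervention to 14 randomized inpatient units at 2 sites", seven per hospital. Start periods are allocated to pairs of units: "we will generate a set of uniform random numbers for each of the seven clusters to be assigned to a starting period".

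Section 12.3 sets a two-sided 0.05 level for all hypothesis tests. No small-sample correction is stated anywhere in the plan.

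**The concern.** Each hospital belongs to a different health system (Section 5 names them, and Section 12.2 splits the required sample per health system). Site and health system are therefore the same two-level factor, and every reading of the and/or yields two clusters. A statistician who codes the primary model from its own paragraph would build the sandwich variance from two contributions. One who codes it from the general paragraph would use 14.

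The two analyses can give very different standard errors and p-values for the same data, and the plan does not say which paragraph governs. At stake are the validity of the primary p-value and confidence interval, and the possibility that the level is chosen after the data are seen.

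**Working it through.** **The plan's own figure.** The documents give no error rate for this model beyond the nominal two-sided 0.05, so that is the benchmark.

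**Step 1: number of clusters.** Site or health system: G = 2. Hospital unit: 2 × 7 = 14. The seven allocated pairs in Section 5 are randomization sequences; the plan does not offer them as an analysis level.

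**Step 2: closed form for G = 2.** Suppose the two hospitals carry equal information, and let d1 and d2 be their separate effect estimates.

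- Pooled estimate: (d1 + d2)/2.
- Uncorrected sandwich variance: the sum of squared deviations from the mean over G², that is [(d1 − d2)²/2]/4 = (d1 − d2)²/8.
- Test statistic: z = [(d1 + d2)/2] / [|d1 − d2|/√8] = √2 × (d1 + d2)/|d1 − d2|.
- Under no effect, (d1 + d2)/|d1 − d2| follows t on 1 df, so z = √2 × t(1).
- False-positive rate: P(|t(1)| > 1.96/√2) = 1 − (2/π) × arctan(1.386) = 1 − 0.6366 × 0.9458 = **39.8%**.

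The ICC and the number of patients cancel out of this result. With a G/(G−1) factor, the rate is 1 − (2/π) × arctan(1.96) = 30.0%. With that factor and a t(1) reference it is 5%, at a critical value of 12.7.

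**Step 3: simulation under no effect.** There were 1,500 trials per scenario, with 14 units, 7 sequences, 8 periods, a 25% base rate and period effects in a logistic GEE. Total N was about 15,000 (Section 12.2's anticipated records; 15,000/112 ≈ 134 per unit-period) or about 2,394 (its required minimum; about 21 per unit-period). ICC 0.01 is the plan's value. ICC 0.05, equal cell sizes and a cluster autocorrelation of 0.8 in one scenario are assumptions.

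| Test, nominal 5% | False-positive rate |
|---|---|
| Robust z, clustered on 2 hospitals, uncorrected | 38.7–40.9% |
| Same, G/(G−1) and t(1) | 4.7–5.1% |
| Robust z, clustered on 14 units, uncorrected | 8.9–14.1% |
| Same, G/(G−1) and t(13) | 6.1–9.1% |
| Model-based, exchangeable within unit, constant unit effect | 5.3–6.3% |
| Same, unit effect varying by period | about 9.5% |

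Simulation error is about ±2.5 points near 40% and ±1.6 points near 10%.

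**Step 4: power left with two clusters and t(1).** The planned 25% versus 35% is a log odds ratio of ln(0.35/0.65) − ln(0.25/0.75) = 0.480. The simulated standard deviation of the hospital-clustered estimate was 0.113–0.120 (N 15,000, ICC 0.01), 0.235 (N 15,000, ICC 0.05) and 0.162 (N 2,394, ICC 0.01). Dividing gives noncentralities of about 4.2–4.0, 2.0 and 3.0. The probability that a noncentral t on 1 df exceeds 12.7 in absolute value is then about 25–26%, 13% and 18%. The plan's target is 80%.

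**The case against.** The strongest reply is that Section 12.3 has already settled the level. Its general paragraph speaks for the whole study, "with the hospital unit as the primary clustering variable", and agrees with the stated level of randomization. The Aim 2b text also describes clustering within clinical unit and hospital and refers back to the same methods. On this view, site in the primary-outcome sentence is loose wording for unit; otherwise its and/or would join two names for one factor.

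Much of this stands. The plan does not commit to two clusters, and its intention is probably the unit. But Section 5 uses sites for the two hospitals, so the literal reading is an ordinary one, and it sits in the only paragraph that specifies the primary model. The general paragraph also keeps health system in play as a clustering variable.

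A reader might go further and infer that the trial's primary test has a 40% error rate, or that both modelling options are invalid. The documents support neither. The 40% belongs to one literal reading with an uncorrected robust z test. The site and health-system wording attaches to the GEE option; the random-effects option names no level, so the general statement about units can govern it. A model with hospital only and no unit effect, tested with model-based variance, gave 13% (N 2,394, ICC 0.01), 40.5–42.9% (N 15,000, ICC 0.01) and 69% (N 15,000, ICC 0.05), but the plan never specifies that model.

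**Conclusion.** The primary-outcome sentence contradicts the general methods paragraph and the level of randomization, and should be corrected before analysis. Followed as written with an uncorrected robust z test, it has about a 40% two-sided false-positive rate. That figure assumes the two hospitals carry equal information; it did not depend materially on ICC or sample size in the range examined. The t(1) remedy controls the error but leaves roughly 13–26% power for the planned 10-point difference, under the assumptions in Step 4.

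This is a conflict between two passages with a serious consequence if resolved the wrong way. It is not a finding that the plan as a whole has a 40% error rate. Naming the unit removes most of the problem but not all of it: an uncorrected robust GEE on 14 units still gave about 9–14%, a result that rests on equal cell sizes, categorical period effects and the assumed ICC and autocorrelation values.

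**What to change.** In the primary-outcome paragraph of Section 12.3:

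1. Replace the site and health-system wording with the hospital unit (14 units) as the level for the GEE or the random effect.
2. Enter the two hospitals as a fixed effect, and do not use hospital or health system as the clustering level for the robust variance.
3. If GEE is used, specify a small-sample variance correction with a t reference. The simple G/(G−1) factor with t(13) still left about 6–9% in these simulations, so a bias-corrected sandwich such as Kauermann–Carroll or Mancl–DeRouen is worth checking by simulation before it is fixed in the plan.
4. State in advance whether GEE or the random-effects model is primary.

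The secondary EHR outcomes inherit the change through their reference to similar procedures. The cost is a sentence or two in the plan and a wider confidence interval than an uncorrected robust analysis would tend to show. No data collection changes.

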12.3 Statistical Methods

Statistical Analysis: For the primary analyses of the primary and secondary outcomes, there will be no crossover of data for subjects from usual care to the intervention during the study; that is, subjects will only contribute data once during the course of the study, from their index hospitalization. Similarly, patients who move units during the course of their index hospitalization will be assigned to contribute intervention time data if they spend at least eight daytime weekday hours after being identified as meeting the inclusion criterion on a clinical unit where the intervention is being conducted. Accordingly, data being contributed by patients at each site during the pre-intervention period and data being contributed by patients after the initiation of the intervention will be kept separate for initial analyses. However, because we expect some patients to have multiple hospitalizations during different steps or to different units (i.e., crossover design), we will perform secondary analyses on all outcomes including data from the index hospitalization. This will include stratified sensitivity analyses of patients who contribute data (a) only to control period; (b) only to intervention period; or, (c) to both control and intervention periods.

Given the randomized nature of the stepped wedge design, we will report our results according to CONSORT guidelines. For the aims of the study that require patient/caregiver enrollment (Aim 2), we will record the number of people approached, screened, ineligible, and refusing participation. We will record subject attrition and note all adverse events. We will employ the intent-to-treat principle in our comparative analyses between the intervention and usual care groups. All hypothesis tests will employ a two-sided alpha level of 0.05. Given that the primary aim will be addressed by the analysis of data obtained from available patient records for the study period, we will examine the distributions of relevant variables focusing on the data relating to the documentation of ACP, the outcome of this aim. For the secondary aims of the study that will require enrollment of a caregiver sample for interview (Aim 2), we will examine the

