We will conduct analyses related to potential effect modification as a step in our model validation process and to identify relationships that can be examined more fully in future research. Should interactions not be found to be statistically significant, we will fit a main effects-only model and use it to formally evaluate confounding by applying a change-in-estimates approach, with a 10% change in estimates being an initial screening criterion. **Secondary outcomes:** Similar procedures will be undertaken to assess intervention effects for the other EHR derived outcomes (documented orders for resuscitation preferences, palliative care consults, hospice enrollment, and documented health care proxies).

For our primary analysis, we will consider our primary outcome (ACP documentation) and our secondary outcomes (resuscitation preferences, palliative care, hospice use, and health care proxies) only for the patient's index hospitalization. However, because we expect some patients to have multiple rehospitalizations during the same step and may also include intervention time (i.e., crossover design), we will perform secondary analyses on all of our primary and secondary outcomes for each patient reviewing all EHR records from the index hospitalization of the patient until their death (or through study period). We will also perform stratified sensitivity analyses of patients who contribute only to control period vs. patients who contribute only to intervention period vs. those that contribute to both control and intervention periods.

We will conduct the above analyses on all Aim 1 and Aim 2a patients for the study primary and secondary outcomes.

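### The primary-outcome model depends on at least five uncorrected interaction tests, and the plan does not say which contrast decides the trial if one is significant

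*Combined protocol and SAP*

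**What the plan says.** All of this is in section 12.3 (Statistical Methods) of the combined protocol and SAP.

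- Significance level: "All hypothesis tests will employ a two-sided alpha level of 0.05". No multiplicity adjustment is given for the interaction tests.
- Modifiers: "Candidate effect modifiers will be specified a priori and will include age, gender, race/ethnicity, religion, and language". Five are named, and the wording makes five a minimum.
- If an interaction is significant, under the primary outcome: "Statistically significant interactions with the intervention will be retained and the nature of heterogeneous intervention effects will be estimated using the interaction model".
- If none is: "Should interactions not be found to be statistically significant, we will fit a main effects-only model and use it to formally evaluate confounding", by a 10% change-in-estimate screen.
- Stated purpose of the effect-modification work: "as a step in our model validation process and to identify relationships that can be examined more fully in future research".
- Expectation: the text says that no effect modification is expected, and then, for race and ethnicity, "we anticipate that this intervention may be particularly beneficial for African-American and Hispanic patients".

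The same paragraph on the primary outcome opens by giving the logistic model the task of estimating and testing intervention against usual care, with no condition attached. Similar procedures are then extended to the four other EHR outcomes. Section 12.2 powers one overall contrast, 25% versus 35%, and makes that 10-point difference the benchmark for clinical significance.

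**The concern.** The two conditional sentences form a data-driven fork in the analysis of the primary outcome. One arm ends in an interaction model, the other in a main-effects model, and a family of at least five tests at 0.05 chooses between them.

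The arms do not deliver the same quantity. Once an intervention-by-modifier term is in the model, the coefficient on intervention is the effect in the modifier's reference category (for continuous age, the effect at age zero unless age is centred). It is no longer the overall difference used for the sample size and the clinical benchmark. The plan does not say whether that coefficient, the stratum effects, an average over strata or a separate overall test is then the trial's result. The confounding screen is also tied to the main-effects model, so it has no stated model on the interaction arm.

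Two things are at stake: a primary result fixed before the data are seen, and protection against reporting chance subgroup effects as findings. The second matters most for race/ethnicity, where an anticipated benefit is already written down and a chance result could be taken as confirmation.

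**Working it through.** **The plan's own figures.** The plan gives no error rate for the interaction tests, so there is none to reproduce. The nearest figure is the sample size for the overall contrast in section 12.2. A pooled two-proportion calculation for 25% versus 35% at two-sided 0.05 gives 329 per group at 80% power and 440 at 90%. The stated 440 is therefore the 90% figure, not 80%. The multiplication holds: 440 × 2 × 2.72 = 2393.6, or 2394. This discrepancy is conservative and has no bearing on the present point. What matters here is that the powered quantity is a single overall effect.

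**Chance of entering the interaction branch.** Inputs from section 12.3: k = 5 modifiers, 0.05 per test. Assumption: no true interaction.

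- Independent tests: 1 − 0.95^5 = 22.6%.
- Five equally correlated test statistics: 18.2% at correlation 0.5, 14.9% at 0.7, 12.7% at 0.8.
- Only race/ethnicity, religion and language correlated: 22.0% at 0.3, 19.6% at 0.7.
- Stepped-wedge simulation (14 units, 8 periods, 3,000 patients, ICC 0.01, common effect 25% to 35%, assumed modifier prevalences, one joint test per modifier, 600 runs): 24.3%, Monte Carlo standard error 1.7 points. Clustering does not remove the effect.
- If category terms were tested singly, which the plan leaves open: about 39% in the same simulation. For ten independent terms, 1 − 0.95^10 = 40%.

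Sample size does not help. These are false-positive rates, so they are the same with 15,000 records as with 3,000.

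**What the branch does to the trial's conclusion.** This needs a rule for reading the retained model, and the plan states none, so three were tried. Simulation set-up: no intervention effect, 9,000 independent patients, 25% documentation, five unrelated modifiers (2, 2, 4, 4 and 3 levels, or all binary), 3,000 trials, clustering ignored. The branch was entered in about 22% of trials.

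| What is read as the trial result | False-positive rate |
|---|---|
| Overall effect, main-effects model always used | about 5% |
| Precision-weighted average effect from the retained interaction model | about 5% |
| Reference-category coefficient of a retained interaction model | about 12% |
| Any significant stratum effect of a retained modifier | 19% (binary) to 22% (mixed levels) |

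So the fork alone does not inflate the overall test. The inflation comes from what is read off the model after the fork.

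**With adjustment, for comparison.** At 0.01 per test (Bonferroni), 1 − 0.99^5 = 4.9%.

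**The case against.** The best defence is that the overall test was never made conditional. The primary analysis is introduced without reference to interactions, the hypotheses in section 12.1 are overall hypotheses, and section 12.2 fixes an overall benchmark and says that effect sizes matter more than p-values. The interaction model is said to estimate the nature of heterogeneity, not to supply the primary test. The main-effects model is introduced for assessing confounding. The modifiers are named in advance, and the stated purpose is model validation and future research.

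Much of this stands, and it rules out stronger readings that a reader might infer:

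- That the trial drops its overall comparison when an interaction is significant. No sentence says so.
- That the primary type I error is about 22%. That holds only if any significant stratum effect counts as the trial's result. Tested as an overall or average effect, it stays near 5%.
- That across five outcomes and five modifiers there is a 72% chance of a false interaction (1 − 0.95^25). This assumes independent outcomes, but the primary outcome in section 4.2.1 itself includes code status, palliative care and hospice documentation. With overlap of that kind, 72% overstates the chance.

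A significant race/ethnicity interaction would also not have to be chance, since the plan anticipates a difference there.

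The defence does not supply the missing statement. Nothing says that the overall effect is reported and tested regardless. An exploratory purpose also sits badly with a rule that keeps significant terms in the model for the primary outcome. Naming the modifiers in advance does not control error across five uncorrected tests.

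**Conclusion.** The point holds as a defect in fixing the primary model and contrast. The form of the primary-outcome model turns on at least five uncorrected tests. With no true interaction, about 1 trial in 5 takes the interaction branch by chance: 22.6% if the tests are independent, roughly 13% to 20% if they are moderately to strongly correlated. These figures assume five joint tests, one per modifier; more modifiers or term-by-term testing would raise them.

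On that branch the deciding contrast is unstated, the intervention coefficient is not the powered contrast, and chance subgroup effects may be reported. The documents do not establish that the overall test is lost or that its error rate exceeds 5%. The 12% to 22% range applies only under reading rules that the plan neither states nor excludes, and it comes from a simulation with assumed modifiers and no clustering.

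**What to change.** In section 12.3, under the primary outcome:

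1. State that the primary result is the intervention effect from the model without intervention-by-modifier terms, with time and clustering included, tested at two-sided 0.05 whatever the interaction tests show.
2. Delete the rule that retains significant interactions in that model, and remove the condition on fitting the main-effects model.
3. Fit each pre-specified interaction in a separate model with one joint test per modifier, report all of them whether significant or not, and label them exploratory, in line with the purpose the section already gives.
4. Adjust for multiplicity only if a confirmatory subgroup claim is intended, for example for race/ethnicity. The choice of method can be left to the sponsor.
5. Apply the same rule to the four secondary EHR outcomes.

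The cost is wording only: no new data and no change to the sample size. The downside is that a true interaction is reported beside the overall effect, not in its place.

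### The primary model for ACP documentation has no prespecified adjustment set, and a main-effects model is promised only if no interaction is significant

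*Combined protocol and SAP*

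**What the plan says.** All of this is in section 12.3 unless noted.

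- **Model.** For the primary outcome, "we will employ logistic regression models for correlated binary outcome data". Clustering is handled "via generalized estimating equations (GEE) or the inclusion of a random effects terms", with no choice made between the two.
- **Covariates.** They are optional: "confounding variables, or covariates can be added to this model as fixed effects". No adjustment list is given.
- **Balance step.** "Variables found to differ between the study groups will be further evaluated to assess their confounding effects". What counts as differing is not defined.
- **Interaction step.** "Candidate effect modifiers will be specified a priori and will include age, gender, race/ethnicity, religion, and language". These five are effect modifiers, not an adjustment set. Then "Statistically significant interactions with the intervention will be retained", and heterogeneous effects are estimated from that interaction model.
- **Main-effects step.** "Should interactions not be found to be statistically significant, we will fit a main effects-only model". Confounding is then assessed by "applying a change-in-estimates approach, with a 10% change in estimates being an initial screening criterion". Whether the 10% refers to the odds ratio or to its logarithm is not stated.

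Some elements are fixed: the secular trend enters regardless of the screen, hospital unit is the primary clustering variable, and tests are two-sided at 0.05. The EHR-derived secondary outcomes follow similar procedures. Section 12.2 sets the benchmark for clinical significance as an absolute rise from 25% to 35%, and gives effect size more weight than p-values.

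**The concern.** No unadjusted model and no fixed-covariate model is designated as primary. Three steps use the trial data to decide which covariates enter and whether the result is one effect or several. Two analysts following section 12.3 on the same data could report different primary odds ratios.

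This matters more here because section 12.2 rests the interpretation on the size of the effect. An estimate to be read against a benchmark should come from a model fixed before the outcomes were seen.

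The 10% screen has a further weakness in a logistic model. Odds ratios are non-collapsible: adding a prognostic covariate moves the treatment odds ratio even when that covariate is exactly balanced. The screen can therefore take prognostic strength for confounding.

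**Working it through.** The plan has no figure of its own for this point, so there is none to reproduce. The inputs are the 25% and 35% rates (section 12.2), and the two-sided 0.05 level, the five named modifiers and the 10% threshold (section 12.3). Covariate strengths and prevalences are assumptions, because the documents give none.

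**1. Paths through the plan**

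| Data show | Model that follows | Single primary effect defined? |
|---|---|---|
| A significant interaction | Interaction model retained | No |
| No significant interaction | Main-effects model, covariates chosen by balance and the 10% screen | Yes, but its covariates are known only afterwards |

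**2. Chance of a false interaction**

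With one test per modifier, all null and independent: 1 − 0.95^5 = 1 − 0.774 = 0.226, about 23%. Positive correlation lowers this, to 5% in the limit where the five tests coincide.

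**3. Can the screen fire with no confounding?**

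Marginal odds ratio = (0.35/0.65)/(0.25/0.75) = 1.615; log = 0.480.

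Take a binary covariate with prevalence q in both groups and outcome odds ratio o. In each group, solve (1 − q)·expit(a) + q·expit(a + ln o) = p, with p = 0.25 or 0.35. The conditional log odds ratio is a(0.35) − a(0.25).

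Hand check with q = 0.5, o = 4:
- Intervention: stratum risks 20% and 50%, mean 35%.
- Control: stratum risks 12.87% and 37.13%, mean 25%.
- Conditional odds ratio = (0.20/0.80)/(0.1287/0.8713) = 0.2500/0.1477 = 1.693; log = 0.5265.
- Change: 0.5265/0.4796 − 1 = 9.8% on the log scale; 1.693/1.615 − 1 = 4.8% on the odds-ratio scale.

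Change in the estimate with exact balance:

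| Covariate OR | q = 0.3, log OR | q = 0.3, OR | q = 0.5, log OR | q = 0.5, OR |
|---|---|---|---|---|
| 2 | 2.3% | 1.1% | 2.5% | 1.2% |
| 4 | 10.2% | 5.0% | 9.8% | 4.8% |
| 5 | 14.1% | 7.0% | 13.1% | 6.5% |
| 6 | 17.8% | 8.9% | 16.0% | 8.0% |
| 8 | 24.8% | 12.7% | 21.1% | 10.7% |

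Covariate odds ratio at which the change reaches 10%:

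| Prevalence | log-OR scale | OR scale |
|---|---|---|
| 50% | 4.1 | 7.5 |
| 30% | 4.0 | 6.6 |
| 20% | 4.6 | 8.0 |
| 10% | 7.4 | 19.3 |

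**4. Illustrative stepped-wedge simulation**

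Set-up: 14 units, 8 periods, ICC about 0.01, unit and period as fixed effects, and five normal covariates independent of treatment. With a treatment effect present, a covariate whose linear-predictor SD was 0.8 passed the screen in these shares of trials:

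| Scale | N about 2,350 | N about 14,900 |
|---|---|---|
| log OR | 53% | 39% |
| OR | 7% | 0% |

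These shares mix non-collapsibility with chance imbalance.

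With no treatment effect, rejection without and with the log-scale screen was 7.3% and 6.0% at N about 2,350 (300 runs), and 3.8% both ways at N about 14,900 (80 runs). The Monte Carlo standard error around 5% is √(0.05 × 0.95/300) = 1.3 points and √(0.05 × 0.95/80) = 2.4 points respectively.

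**The case against.** **The model is not wholly open.** Time and unit clustering are fixed, and 10% is described only as a first screen. This stands, but neither point supplies the adjustment set.

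**The interaction work is exploratory in spirit.** Section 12.3 expects no effect modification and presents these analyses as model validation and leads for later research. No passage says that the overall effect will go unreported, so a reader should not infer that. What remains is that the text makes the main-effects model conditional on non-significant interactions and does not say which estimate is primary otherwise.

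**Non-collapsibility is a change of target, not bias.** Correct. A covariate forced into the model would shift the odds ratio just as much. Prespecification cures data-driven selection; it does not remove non-collapsibility.

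**Only strong covariates trip the screen this way.** Correct for a single covariate with exact balance. An odds ratio of 2 moves the estimate by 2.5% at most, and on the odds-ratio scale even 6 stays under 10%.

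**Two stronger readings a reader might infer are not supported:**
- *Inflated type I error.* Non-collapsibility causes no shift under a true null, and the simulation showed no inflation. Its runs are few and cover only the 10% screen, so they do not prove its absence either.
- *Selection that always enlarges the effect.* With a real effect, non-collapsibility moves the odds ratio away from 1, but the screen also reacts to chance imbalance, which can go either way.

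**Conclusion.** The point holds as a gap in prespecification that should be closed. Section 12.3 states a data-driven rule for the covariates and form of the primary model and designates no fixed model as primary.

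- **Firm from the text:** the primary odds ratio is not defined until outcome data are seen, and no single primary effect is defined if an interaction is significant.
- **Up to about 23%:** the chance of reaching that second situation through a false positive, assuming five independent tests at 0.05.
- **Conditional on assumed covariate strength:** the screen can fire without confounding at an outcome odds ratio of about 4 (log scale) or 6.6 to 7.5 (odds-ratio scale) at 30–50% prevalence. The documents do not show whether any EHR covariate is that strong, or which scale applies.

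Neither an inflated error rate nor a one-directional bias is part of this conclusion.

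**What to change.** In section 12.3:

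1. Designate one main-effects logistic model as primary. It contains intervention phase, period, hospital, clustering by unit (one method named), and a listed set of EHR covariates that precede exposure, for example age, gender, race/ethnicity and language. Keep all of them regardless of balance or change in estimate.
2. Include dementia or delirium only if recorded before exposure. Delirium can arise or be recorded during the admission, so adjusting for it without that restriction risks conditioning on a post-exposure variable.
3. Remove the balance check and the 10% screen as selection rules for the primary model. They may stay as sensitivity analyses, with the scale of the 10% stated.
4. State that the main effect stays primary whatever the interaction tests show, and report interactions as exploratory.
5. Because the section 12.2 benchmark is an absolute 10 points, also report the standardised risk difference from this model.
6. Apply the same rules to the EHR-derived secondary outcomes.

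Cost: SAP wording and a small amount of extra analysis. No sample size or data collection changes.
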